Hypothesis: IM epinephrine is an efficacious adjunct to inhaled bronchodilators (β_2 agonists) for children with severe asthma exacerbation.

Methods:

Study design: This is a repeated measures, parallel group, single-blinded randomized controlled therapeutic trial.

Study site: Kosair Children's Hospital emergency department

Eligible participants: The study population will be comprised of children age 6-17 years old who present to the ED with severe status asthmaticus as diagnosed by the treating provider and verified by peak expiratory flow rate (PEFR) of <60% of predicted prior to intervention or a clinical asthma score of 7 or greater.

Inclusion criteria

- 1. Age greater than 6 years and less than 18 years
- 2. Pre-existing diagnosis of asthma
- 3. Presenting to the ED with an asthma exacerbation

Exclusion criteria

- 1. History of chronic lung or upper airway disease other than asthma
- 2. History significant, uncorrected congenital heart disease or cardiac arrhythmia
- 3. History of thyroid disease, stroke, sickle cell disease, or renal disease
- 4. Systolic blood pressure greater than the 95th percentile for height, age, and gender
- 5. Impending respiratory failure
- 6. Allergy to epinephrine
- 7. Pregnancy
- 8. Weight < 20 kg

Screening procedures: Patients presenting to the ED for asthma exacerbation who meet the inclusion criteria will be considered for enrollment in the study. A brief form will be completed by a study investigator or research assistant to assess for eligibility.

To accurately ascertain predicted PEFR, height will be measured. PEFR testing will be performed by respiratory therapists (RT) in the ED once the patient is brought into a treatment room. The RT will also measure the clinical asthma score.

Girls who meet all of the other screening criteria will be asked if they have achieved menarche. If so, they will be asked to give a urine sample so that a pregnancy test can be performed.

Consent procedures: The study will be described in detail initially. If the parents and patient would like to participate, then a research member will discuss the informed consent and assent (if applicable) with the families and obtain signatures.

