Baseline data: Once screened, consented, and enrolled, the following demographic data will be collected: birthdate, gender, race, time of arrival to the ED, details of any treatment by a referring provider, symptom type and duration (hours), time since last inhaled bronchodilator (minutes), time since systemic corticosteroids (minutes), number and type of inhaled bronchodilator treatments in the preceding 24 hours, all home medications, drug and food allergies, past medical history, number of hospital admissions for asthma over the prior 12 months, and number of ICU admissions over the child's lifetime. Initial temperature, respiratory rate, heart rate, blood pressure, and pulse oximetry will be recorded. Finally, height, PEFR, and CAS will be measured by the respiratory therapist (RT) immediately prior to the study intervention. Additionally, the subject's family will be asked to complete an Asthma Control Tool (ACT). The ACT is a measure of how well the participant's asthma has been controlled over the preceding three months.

Intervention: Subjects will then be randomly assigned (50% chance) to receive a weight based dose of IM epinephrine 1:1000 or no adjunctive medication. The dose will be 0.2 mg for subjects 20-30 kg and 0.3 mg for subjects greater than 30 kg. This will be injected intramuscularly by an ED nurse into the anterior thigh muscles of the subject using a 1 ml syringe and a 23 gauge one inch needle.

In addition to the study intervention, the standardized treatment pathway based on the current asthma guidelines in use at our center will be utilized. This pathway includes nebulized albuterol, ipratropium bromide, and systemic corticosteroids. The duration and dosages of these other interventions will be administered at the discretion of the treating provider.

Randomization: A block randomization scheme will be used to promote balance at the end of the study. Block randomization ensures that after each block of individuals are enrolled in the study (n individuals in total); an equal number of individuals will be assigned to each group (n/2 individuals in each group). We will use random block sizes of 8-12.

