Allocation concealment: The RT will be blinded as to whether the subject receives a dose of IM epinephrine. Once a patient is determined to be eligible for the study, the research team will complete informed consent/assent. A pharmacy generated randomization schedule will be utilized and sealed envelopes with the allocations (treatment or control) will be kept in the charge nurse's office.

At the time of allocation, the charge nurse will instruct all staff to leave the subject's room. The charge nurse will then open the designated envelope and personally prepare and administer IM epinephrine if the subject is allocated to the treatment arm. If the subject is allocated to the control arm, the charge nurse will draw up a syringe with the appropriate amount of saline as if an injection of epinephrine was going to be given to the participant. The charge nurse will take this syringe into the subject's room, but not administer it. Instead, a 'sham' Band-Aid will be placed over the thigh of the subject. They will be instructed not to reveal to the RT, research team, or bedside nurse whether or not an injection was actually given. Participants and families will be similarly instructed. The RT will remain blinded throughout and will be responsible for measuring all PEFRs and CASs.

Having block sizes that are randomly determined, as well as having larger block sizes of 8-12 will help minimize a member of the research team or the RT guessing the allocation of the next participant and potentially biasing recruitment or assessment. To further assess blinding, at the conclusion of the study, we will ask the RTs to guess which group the subjects they assessed were in.

Study data: The following data will be measured at time points (t_{15} , t_{30} , t_{60} , t_{90} , and t_{120}) minutes following IM epinephrine or sham drug administration: PEFR (if able), CAS, heart rate, respiratory rate, and pulse oximetry. This data will also be recorded at the time of discharge or admission from the ED. Also recorded will be amount and timing of bronchodilator, anticholinergic, and corticosteroid therapy given. Additionally, any other therapies and interventions will be recorded (i.e. oxygen administration, assisted ventilation, magnesium sulfate administration, etc.). ED length of stay as well as disposition will be noted.

Primary outcome measure: Change in percent of predicted PEFR/CAS 15 minutes after the study intervention (t_{15}).

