Secondary outcome measures:

1. Change in percent of predicted PEFR/CAS at t₁₅

- 2. Disposition
- 3. Change in percent of predicted PEFR/CAS at t₃₀, t₆₀, t₉₀ and t₁₂₀
- 4. Change in percent of predicted PEFR/CAS at t₃₀, t₆₀, t₉₀ and t₁₂₀
- 5. Change in respiratory rate at t_{15} , t_{30} , t_{60} , t_{90} and t_{120}
- 6. Change in heart rate at t_{15} , t_{30} , t_{60} , t_{90} and t_{120}
- 7. Need for supplemental oxygen at t_{60} , t_{90} and t_{120} (defined as a room air pulse oximetry of <93%)
- 8. Need for albuterol at t_{60} , t_{90} and t_{120}
- 9. Number of hours of albuterol therapy
- 10. ED length of stay

Statistical analysis plan: First straightforward tests for differences among the two groups of individuals will be performed. Analysis of Variance (ANOVA) techniques will be used to test for differences among continuous variables, while Kruskal-Wallis, Fischer's Exact Tests and Wilcoxon methods will be used to test for differences among categorical variables. To examine the outcomes of: (1) change in percent of predicted PEFR/CAS, (2) respiratory rate, (3) heart rate, (4) hours of albuterol therapy and (5) length of stay in the ED, separate mixed-effects general linear models will be developed for each outcome (five models will be developed). The two arms (IM epinephrine and no epinephrine) will be analyzed as fixed effects, and time (time since randomization) will be analyzed as a repeated measures effect. Traditional risk factors (e.g. age, gender, and ethnicity) will be incorporated as covariates during secondary analyses. All main effects and all two-way interaction effects will be investigated for significance from the mixed-effects models developed. Negative binomial regression and logistic regression techniques will also be used to evaluate (7) need for supplemental oxygen and (8) need for albuterol. Life table analysis and Kaplan-Meier techniques will initially be used to analyze the time-related variables (e.g., time to discharge). The Log-rank test will be used to test for differences among survival curves. In addition, Cox (proportional hazards) regression techniques will be developed to test for differences among groups as well as allow for adjustment for additional covariates and risk factors. Cox regression will allow us to investigate all potential main effects and interaction effects. All statistical analyses will be performed by a statistician who is blinded to the treatment allocation of the two groups.

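### The treating provider is not among those from whom allocation must be withheld, leaving two secondary outcomes directly, and two more by inference, open to performance bias

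*Combined protocol and SAP*

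**What the plan says.** The Study design paragraph states: "This is a repeated measures, parallel group, single-blinded randomized controlled therapeutic trial". The Allocation concealment section describes a careful procedure. When the envelope is opened, "the charge nurse will instruct all staff to leave the subject's room". A child in the treatment arm is injected. For a child in the control arm the charge nurse carries in a saline syringe, does not use it, and puts a Band-Aid on the thigh.

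On later disclosure the section says: "They will be instructed not to reveal to the RT, research team, or bedside nurse whether or not an injection was actually given". It continues: "Participants and families will be similarly instructed". The outcome assessor is dealt with explicitly: "The RT will remain blinded throughout and will be responsible for measuring all PEFRs and CASs". The end-of-study check on blinding asks only the RTs to guess the arm.

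The Intervention section sets a standardized pathway of albuterol, ipratropium and systemic corticosteroids, and adds: "The duration and dosages of these other interventions will be administered at the discretion of the treating provider".

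The secondary outcomes include disposition (item 2), need for albuterol at 60, 90 and 120 minutes (item 8), "Number of hours of albuterol therapy" (item 9) and "ED length of stay" (item 10).

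**The concern.** The instruction names three parties, and the person with discretion over co-treatment is not one of them. A provider who knows that epinephrine was given might continue albuterol for longer or shorter, keep the child under observation, or admit more or less readily. A difference between arms in albuterol use, disposition or length of stay could then reflect the provider's response to the allocation rather than the drug.

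These outcomes are formally tested. The statistical analysis plan assigns mixed models to hours of albuterol and length of stay, logistic or negative binomial regression to need for albuterol, and Kaplan-Meier, log-rank and Cox methods to time to discharge. Blinding the statistician, which the plan provides for, cannot remove a bias that arose at the bedside.

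**Working it through.** The plan states no figure on this point, so there is none to reproduce. The check has two parts.

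**1. Who may learn the allocation, and what they decide**

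| Role | Covered by the do-not-reveal instruction? | Part in the outcomes |
|---|---|---|
| RT | Yes; also stated to stay blinded | Measures all PEFR and CAS values |
| Research team | Yes | Screening and consent |
| Bedside nurse | Yes | Not specified for outcomes |
| Treating provider | Not named | Discretion over co-treatment |

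The charge nurse always knows the arm. A control child gets no needle, so the child, and any relative who is watching, can know it too. Clearing the room stops the provider from seeing the injection; it does not govern what is said afterwards. A provider who is also an investigator falls under the research team and is covered. Other ED providers are not.

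Sorting the secondary outcomes by exposure:

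- Directly exposed on the text: items 8 and 9. The provider controls the duration and dosages of albuterol, and need for albuterol has no objective definition.
- Exposed by inference: items 2 and 10. The protocol names no decision-maker and gives no criteria for admission or discharge, so provider judgement is the natural reading but is not stated.
- Indirectly exposed through co-treatment: items 3 to 6 (PEFR/CAS after 15 minutes, respiratory rate, heart rate).
- Less exposed: item 7, since need for oxygen is defined by room-air oximetry below 93%.

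The count is therefore two explicit plus two inferred.

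**2. Illustration of size**

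Inputs: 54 analysed participants (Power calculation section), taken as 54/2 = 27 per arm; two-sided 0.05. Assumed, because the documents give no values: no drug effect, 60% admission without the bias, and a shift s in one arm caused only by provider knowledge.

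For admission, the rejection rate is the sum, over all pairs (a, b) for which Fisher's two-sided p is below 0.05, of Bin(a; 27, 0.60) × Bin(b; 27, 0.60 − s):

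| Shift s (percentage points) | Admission rates | Trials with p<0.05 |
|---|---|---|
| 0 | 60% v 60% | 2.5% |
| 5 | 60% v 55% | 3.3% |
| 10 | 60% v 50% | 6.2% |
| 15 | 60% v 45% | 11.6% |
| 20 | 60% v 40% | 20.3% |

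Fisher's test is conservative at this sample size, which is why the first row is below 5%.

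For a continuous outcome such as hours of albuterol, with an assumed shift of b standard deviations and a two-sided normal test, the standardised shift is q = b/√(2/27) = b/0.272, and the rejection rate is [1 − Φ(1.96 − q)] + Φ(−1.96 − q):

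| b (SD) | q | Trials with p<0.05 |
|---|---|---|
| 0 | 0 | 5.0% |
| 0.1 | 0.37 | 6.6% |
| 0.2 | 0.73 | 11.4% |
| 0.3 | 1.10 | 19.7% |
| 0.5 | 1.84 | 45.1% |

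Both tables apply the shift to the whole arm. If, say, half the providers learned the allocation and each of them moved admission by 20 points, the arm-wide shift would be 0.5 × 20 = 10 points, and the rate 6.2% rather than 20.3%.

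**The case against.** The strongest reply is that the protocol promises no provider blinding. It calls itself single-blinded, names the RT as the blinded assessor, and has that RT measure the primary outcome. How far to extend the blind is a design choice. Clearing the room, the decoy syringe and the Band-Aid also hide the injection from everyone outside, the provider included. Discretion over co-treatment operates within a standardized pathway. The large error rates above need large shifts across a whole arm; at 5 points the rate remains under 5%, and at 10 points it is only slightly above.

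Much of this stands. It confines the point to secondary outcomes and rules out a firm statement of size. It does not close the gap. The protocol already goes beyond assessor blinding by shielding the bedside nurse and research team, yet omits the role to which it gives discretion over co-treatment. The standardized pathway does not constrain duration or dosage, because the same section leaves those to the provider.

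A reader might go further and infer that providers will be told the allocation, that all four outcomes are stated to be provider decisions, or that the primary result is compromised. The documents do not support these readings. Silence is not a described disclosure; control of disposition and discharge is inferred; and co-treatment within 15 minutes is at most a minor route to an outcome that a blinded RT measures.

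**Conclusion.** The concern holds in limited form. As written, the plan leaves the treating provider outside the do-not-reveal instruction, and provider unblinding would go undetected because only RTs are asked to guess. Need for albuterol and hours of albuterol are directly open to performance bias; disposition and ED length of stay are so by reasonable inference. The 15-minute primary outcome is largely protected.

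The size is unknown. Under the stated assumptions the false-positive rate for admission runs from no excess over 5% at small shifts to about 20% at a 20-point arm-wide shift. These figures show sensitivity and are not an estimate of the bias in this trial. The gap should be closed, but it does not threaten the main comparison.

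**What to change.** In the Allocation concealment section, add the treating provider to those to whom the charge nurse must not reveal the allocation, and give families the same wording. Log every disclosure of allocation to a provider; the route for disclosure on safety grounds is for the sponsor to define. Include treating providers in the end-of-study guess, so that the success of the blind can be judged where it matters for these outcomes. In the analysis plan and report, label the care-dependent secondary outcomes as open to residual performance bias.

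The cost is a few words, a log line and one more group in the blinding check, since all staff already leave the room. The downside is that some providers will ask for the allocation. The change reduces the bias and does not remove it: controls receive no needle, children and families may talk, and a provider may notice the effects of epinephrine, such as the palpitations listed under Risks and benefits or a change in the recorded heart rate.

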Planned interim analysis: Interim analyses, reported to the data monitor will be performed at 6, 9 and 12 months after the first participant is randomized. A Lan-DeMets spending function approach will be used to monitor the need for early trial termination.

Power calculation: We will develop separate mixed-effects general linear models for each of the outcomes. For a sample size (n=54) the study has 81% power to detect a 12% main effect of each treatment for each outcome. The estimated power for detecting a 5% interaction effect is 32%. The total sample size required to achieve 80% power to detect an interaction effect, based on the full-factorial designed proposed, is n=1728; which is not a feasible number in which to recruit and enroll. In addition, we will develop Cox proportional hazards regression models to assess the association between group assignment and time related outcomes. For the anticipated sample size (n=54), this study has 80% power to detect a hazards ratio of 1.82 with two-sided α =0.05. Lastly, multiple logistic regression techniques will be utilized to assess

the association between group assignment and dichotomized outcomes. Using the dichotomized version of some outcomes, this study has 80% power to detect on odds ratio of 1.58 with a two sided α =0.05 (n=54). Therefore, we have more than sufficient numbers of participants in each comparison group.

We anticipate that less than 10% of all potential participants will drop out. Therefore, we will recruit a total of 60 individuals for the current study (n=30 per group). This is a feasible sample size for the research team to recruit and enroll in the current study. Power calculations were based on the anticipated total sample size (n=54) that will be available for complete analysis. Using a block randomization scheme (with random block sizes of 8-12), we anticipate that n=30 participants will be assigned to each group.

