Recruitment plan: A team of medical student research assistants already in place in the ED will be utilized to help with identifying and consenting potential subjects. Moreover, a research assistant dedicated to the study will be recruiting. All children who present to the ED with an asthma exacerbation while an investigator is available will be screened for eligibility. Based on prior experience, an average of five eligible children will present weekly or 20 per month. If five (25%) of these are recruited monthly, recruitment will be completed in 12 months. If three (15%) are recruited monthly, recruitment will be completed in 20 months.

Risks and benefits:

IM epinephrine has been used for years for the treatment of anaphylaxis in the same doses that will be studied. Severe adverse events are exceedingly rare. These include: cardiac arrhythmia and inadvertent injection into the systemic circulation. The latter could cause a transient, but potentially dangerous increase in the subject's blood pressure. Having the entire study take place in a pediatric emergency department where experts in the management of acutely ill children are immediately available further mitigates this exceedingly small risk. There are transient and minor side effects including anxiety, headache, fear, and palpitations that pass quickly.

At the participant level, the investigators believe there is true clinical equipoise with IM epinephrine in severe asthma exacerbation. However, there is biologic plausibility for a systemic drug to help children whose airways are closed off from severe asthma exacerbation. If the treatment works, subjects who receive epinephrine will breathe better more quickly than if they hadn't received the treatment.

At the societal level, demonstrating the utility of a novel, readily available, inexpensive treatment for severe asthma exacerbation would have far reaching effects for literally hundreds of thousands of children.

Data safety monitoring plan: A knowledgeable physician ([name]) who is not a coinvestigator for this study will serve as the study's safety monitor of adverse events. He will review all clinically significant adverse events within 72 hours. Any clinical adverse events noted by the study personal or the clinical team (MD, RN, RT) will be reported to the monitor within 24

hours. All severe adverse events will be reviewed by the monitor as soon as possible and reported to the IRB within 3 business days.

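### The RTs' allocation guess comes at the end of the study, which biases it toward chance, so a near-50% result would not show that blinding held

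*Combined protocol and SAP*

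**What the plan says.** The Allocation concealment section of the combined protocol and SAP makes the RT the blinded assessor: "The RT will remain blinded throughout and will be responsible for measuring all PEFRs and CASs". These are the measurements behind the primary outcome, the change in percent of predicted PEFR/CAS at 15 minutes. In the control arm no injection is given: "Instead, a 'sham' Band-Aid will be placed over the thigh of the subject". Children and families are told not to disclose what happened.

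The same section then adds a check, introduced by "To further assess blinding": "at the conclusion of the study, we will ask the RTs to guess which group the subjects they assessed were in".

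The Study data section lists what is recorded at t15 to t120 and at ED discharge or admission. The guess is not on that list. The Recruitment plan gives two scenarios: "If five (25%) of these are recruited monthly, recruitment will be completed in 12 months" and "If three (15%) are recruited monthly, recruitment will be completed in 20 months". The document gives no don't-know option, no request for a reason, no blinding index and no analysis of the guesses.

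**The concern.** An RT sees a child in the ED for a few hours. If the guess is sought only when the trial ends, it asks for recall of one encounter that may lie many months back. A forgotten encounter yields a coin toss, and coin tosses move the overall proportion correct toward 50%, which is also the figure expected under successful blinding with 1:1 allocation. The error therefore runs in the reassuring direction.

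This matters because the trial is single-blinded. A child in the control arm can tell that no needle was used, and the protocol relies on an instruction not to say so. Epinephrine may also show itself: the Risks and benefits section lists anxiety and palpitations, and heart rate is recorded at every time point. PEFR and CAS both pass through the RT. If readers later ask whether the RT was truly blinded, this guess is the only planned data with which to answer.

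**Working it through.** **Inputs from the document.** Planned recruitment is 60 children, 30 per group (Power calculation). Recruitment is 5 or 3 per month (Recruitment plan). Allocation is 1:1 (Intervention), so a pure guess is right 50% of the time.

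**Inputs assumed, because the document gives none.** These are the proportion correct if asked at once (*p*), the share of that information still recalled at the end (*r*), the forgetting half-life (*h*), independence of the 60 guesses, and even accrual.

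**Step 1: recruitment time.** 60/5 = 12 months and 60/3 = 20 months, which reproduces the plan's figures.

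**Step 2: gap between assessment and guess.** The 12 or 20 months is the gap for the first child enrolled, if the guess is taken when recruitment closes. With even accrual:

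- The mean gap is 12/2 = 6 months or 20/2 = 10 months.
- The share of children with a gap over 3 months is (12 − 3)/12 = 75% or (20 − 3)/20 = 85%.
- The share over 6 months is (12 − 6)/12 = 50% or (20 − 6)/20 = 70%.

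**Step 3: attenuation.** Expected proportion correct = 0.5 + *r*(*p* − 0.5). With *p* = 0.80 and *r* = 0.25, this is 0.5 + 0.25 × 0.30 = 0.575.

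**Step 4: chance of detection.** An exact two-sided binomial test at 5% with n = 60 calls guessing better than chance at 39 or more correct (upper tail 0.0137 under 50%). The chance of reaching 39 is:

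| Recalled share *r* | Correct, *p* = 0.80 | Detection, *p* = 0.80 | Detection, *p* = 0.70 | Detection, *p* = 0.90 |
|---|---|---|---|---|
| 1 (asked at once) | 80% | 99.8% | 84% | over 99.9% |
| 0.5 | 65% | 56% | 26% | 84% |
| 0.25 | 57.5% | 15% | 8% | 26% |
| 0.1 | 53% | 4% | 3% | 6% |
| 0 | 50% | 1.4% | 1.4% | 1.4% |

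**Step 5: the same with gradual forgetting.** Suppose recall decays exponentially, so that *r* is the average of 0.5^(gap/*h*) over the 60 children. With *p* = 0.80:

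| Half-life *h* | 12-month recruitment: correct, detection | 20-month recruitment: correct, detection |
|---|---|---|
| 1 month | 53.6%, 5% | 52.2%, 3% |
| 3 months | 60.1%, 26% | 56.4%, 11% |
| 6 months | 66.2%, 64% | 61.7%, 35% |
| 12 months | 71.6%, 90% | 67.8%, 73% |

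The direction is the same in every row. The size depends on how fast RTs forget, which is unknown.

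**The case against.** **A reader might infer that the guesses will fall to 50% whether or not blinding held.** The documents do not support that. It needs near-total loss of recall for nearly every child, and they say nothing about recall. Late enrolees have short gaps, and with a half-life of 6 to 12 months an 80% rate would still appear as 62% to 72%. What stands is the bias toward 50%, not its endpoint.

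**The timing is not defined.** The conclusion of the study could mean the end of each child's participation. The plural subjects and the absence of the guess from the per-child data list favor the end of the trial, and the Randomization section refers to the end of the study in that sense. The other reading is possible, and the plan should settle it.

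**The check is supplementary.** A reader might infer that the late guess undermines the primary result or shows that blinding failed. It does neither. No analysis or decision rule depends on the guess. Protection comes from the procedures: staff leave the room, one charge nurse opens the envelope, a syringe is carried in for both arms, a sham Band-Aid is placed, and those who know are told not to tell. Moving the guess changes no estimate. This objection stands in full and limits the weight of the point.

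**An early guess has faults too.** Once the RT has seen the child respond, a correct guess may come from improvement or heart rate and not from broken blinding. Asking straight after t15 would also prompt the RT before the t30 to t120 readings, which are secondary outcomes. Both points stand and shape the fix.

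**The 60 guesses are not independent.** Several RTs each guess for several children, so guesses may cluster by RT. The detection figures are illustrative for this reason as well.

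**Conclusion.** The point holds in limited form. Read as an end-of-trial exercise, the guess comes on average about 6 to 10 months after the assessment. Forgetting biases the proportion correct toward 50%, so a near-chance result would be uninformative about whether the RT was blinded. For an assumed 80% correct if asked at once, the chance of detection falls from 99.8% to 56%, 15% or 4% as recall falls to a half, a quarter or a tenth. These figures rest on assumed accuracy, assumed recall, even accrual and independent guesses. The durations and the 50% chance level come from the plan. A clearly high proportion correct would remain evidence that RTs could tell the arms apart, though it would not show how.

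The consequence is confined to an ancillary check. This is a worthwhile, inexpensive improvement and not a defect in the primary analysis.

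**What to change.** Replace the sentence on the RTs' guess in Allocation concealment with: *After each subject's last scheduled RT assessment (t120, or ED discharge/admission if earlier), the RT records a guess (epinephrine / no epinephrine / don't know) and the reason for it. Results are reported by arm with a blinding index.* Add the item to the list in Study data.

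Placing the guess there keeps the prompt away from every PEFR and CAS reading that is a listed outcome. If a discharge or admission reading follows t120, it comes after the prompt, but it is not a listed outcome.

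The cost is one added form item per child. The remaining weakness is that the guess may reflect the child's observed response or heart rate, so the recorded reason is needed to separate that from disclosure or a visible lapse in procedure.
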